#### 6.2.4. *MESA Glucose Homeostasis Exam Components*

- **Continuous Glucose Monitoring:** Participants will be consented and asked to wear a continuous glucose monitor (FreeStyle Libre Pro CGM from Abbott) for up to 14 days. The device may be distributed in clinic, during a home visit, or via mail along with video instructions. Calibration is not needed during wear time. Participants will then be asked to remove the CGM and mail it back to the study site using a prepaid envelope (or return it to study technicians during a home visit). If the CGM is lost or damaged, or if another scientific question arises that could be answered with repeated monitoring, participants may be invited to repeat the monitor. A subset of participants (n=1,000 focused on those with measured amyloid PET) will be asked to repeat the CGM data collection 2 years after Exam 7.
- **Diary Entry:** Participants will be asked to keep a paper diary of their waking, sleeping, and mealtimes. Diary instructions will be distributed along with the CGM. For the subset of participants asked to repeat the CGM collection 2 years after Exam 7 (2024-2025), diary tracking will also be repeated. This diary will be integrated into the logs used by other ancillary studies with wearables.
- **Cognitive Function Testing:** A subset of 1000 participants will be asked to repeat CGM and diary data collection 2 years after Exam 7. All participants complete an abbreviated cognitive assessment by telephone or video call in accordance with standardized and validated MESA-MIND protocols at the same time.

#### 6.2.5. *MESA Neighborhood Exam Components*

- **Neighborhood Questionnaire:** Participants will be asked to complete a Neighborhood Questionnaire. The survey will include measures from previous MESA Neighborhood surveys (aesthetic quality, walking environment, availability of healthy food, safety, social cohesion, physical disorder, social disorder) and novel questions from PACER (Perceptions About Change in Environment and Resources) regarding neighborhood change and aging supports. The survey will take approximately 25 minutes to complete. The survey can be completed in any mode (in-person, tele-visit/remote, web-based, mail, or phone). Participants will be compensated for completing the survey.
- **Calculated Graphic Information System (GIS) measures using anonymized geocodes:** At no additional burden to participants, GIS measures will be collected and processed at Drexel University. Geocoded addresses (i.e. latitude/longitude of resident addresses) will be shared with MESA Neighborhood ancillary studies using an anonymized ID, void of any personal and health data. These will be used to obtain characteristics of participant neighborhoods, such as availability of different kinds of stores, and layout of streets. Only University of Washington will hold the key to reconnect these neighborhood characteristics to participant identifying information.

#### 6.2.6. MESA Sleep Exam Components

- **Sleep Actigraphy Monitoring (Wrist):** Participants will be fitted for a wrist sleep monitor during the Exam 7 clinic visit or home visit, or mailed the device and given telephone instructions. Devices will be programmed before distribution. The wrist sleep monitor device (GeneActiv) will be worn on the nondominant wrist for 8 consecutive days to improve rhythm assessment and to overlap, as possible, both the night of the polysomnography study and 24-hour ABPM (ambulatory BP). The device looks like a wristwatch, has a patient-activated event marker, a rechargeable battery, and light sensor. These features improve the ability to annotate off times and sleep onset/offset and provide high quality light data to allow analysis of light cues in relationship to sleep-wake patterns. The device can be worn during showering and bathing but should be removed during prolonged periods of immersion (swimming). Instructions on returning the device with use of a pre-paid mailer will be provided (unless retrieved at the time of a study technician home visit). Once the watch is returned to the Field Center, a staff member will download the data using commercial software and electronically transfer the data files to the Sleep Reading Center (SRC) via a secure website. Sleep diaries will be concurrently scanned and sent to Brigham and Women's Hospital to be used when editing each record. Participants may be asked to repeat the sleep monitoring if it captures less than 5 days of data or if another scientific question arises that could be answered with repeated activity monitoring.
- **Sleep Diary Entry:** Participants will be instructed on completing a brief daily sleep log for 8 consecutive days (while using the wrist sleep monitor), when waking up daily, recording bed & wake-up times, recording perceived sleep latency, naps, any unusual events during the day or night, ratings of sleep quality, times when the wrist sleep monitor and BP cuff (first night only) is removed. This information will be used to edit the wrist sleep monitor data, provide subjective reports of daily variation in sleep patterns and identify factors that influence night-to-night variability. This diary will be integrated into the logs used by other ancillary studies with wearables.
- **24-hour Blood Pressure Monitoring:** The ABPM (OnTrak; Spacelabs), a lightweight portable device validated for ambulatory blood pressure (BP) measurement, will be applied for 24 hours on a non-dominant arm (unless there is a contraindication to use that arm, for example, related to lymphedema), typically at the end of the physical activity monitoring period, and overlapping with the last day of wrist sleep monitoring. Specifically, ABPM will overlap with the one night of wrist sleep monitoring but not with the home sleep study (polysomnography). After the initial period of in-home activity monitoring, the ABPM, programmed by the MESA research assistants before use and provided with fresh batteries, will be fit during a return home visit (when other equipment is retrieved). Appropriate cuff size will be determined by a trained research assistant after measuring the participants' mid-arm circumference. Cuffs will be secured, a marker placed to allow ease of replacement, and subjects instructed on how to remove them and check for placement. An initial automated BP recording will be made during placement; placement will be rechecked if the automated reading is >15% different than a manual reading. Participants will be instructed on how to carry the monitors using a

shoulder strap or waist band. Devices will be programmed to measure BP at 30 min intervals. Cloth covers for each cuff will be provided to optimize comfort. The ABPM will be retrieved by the research team during a home visit or returned by mail. Once the ABPM is returned to the Field Center, a staff member will download the data using commercial software and electronically transfer the data files to the Sleep Reading Center (SRC) via a secure website. Diaries will be concurrently scanned and sent to Brigham and Women's Hospital to be used when editing each record. If the study does not have sufficient data, or if another scientific question arises that could be answered with repeated ambulatory blood pressure monitoring, the participant will be invited to repeat the study.

- **Polysomnography:** Polysomnography (PSG) is the gold standard for objectively measuring sleep neurophysiology, sleep-related breathing abnormalities and sleep-related movements, providing information not available from wrist sleep monitor. The Nox Medical A1 PSG unit will be used for this home sleep study, which is fully compliant with American Academy of Sleep Medicine (AASM) standards. The device acquires high resolution signal quality through 32-bit signal processing and 256 kHz sampling on all channels and provides advanced noise reduction and anti-aliasing, thus facilitating generation of quantitative metrics. It is designed to be low burden (the bluetooth wrist oximeter has no wires, allowing unrestrained movement). The system is powered by a rechargeable battery and has 1 GB of data collection capacity per study. The montage includes airflow (via a nasal pressure cannula, DC-coupled for linearization), respiratory effort (high resolution thoracic and abdominal inductance plethysmography bands), finger pulse oximetry (Nonin Wrist-OX2 3150), ECG, bilateral frontal, central and occipital EEGs, EOG, and chin and tibialis EMGs. Should a home visit not be possible, a modified version of the NOX A1 device will be mailed or distributed to the participant at the end of the clinic exam for self-application. This modified version contains the same sensors other than the EEG, EOG and chin EMG gold cup electrodes. Instead, the device will have self-applied electrodes for sleep EEG assessment, which can be readily applied using verbal and written instructions and an optional instructional video.
- Methods for instruction and set up will be similar to what was used in the first MESA Sleep exam. Research assistants will review with the participant the purpose of the test, instructions on wearing study equipment, and then apply the sensors. After the home sleep study, the PSG unit will be retrieved by study personnel or courier. The research assistant will upload the sleep study (PSG) to a secure cloud platform using commercial software and accessed by SRC personnel for quality control analysis, standardized scoring, and off-line processing for quantitative phenotypes. To be minimally acceptable, a PSG study should have at least 4 hrs of continuous, predominantly artifact-free tracing on key channels. If sufficient data is not collected, or if another scientific question arises that could be answered with repeated polysomnography, participants may be invited to repeat the polysomnography.
- **Sleep Questionnaire:** All participants will complete a general Sleep Questionnaire at Exam 7. Those ~~with an in-home sleep study~~ who consent to any MESA Sleep monitor (wrist activity, ABPM, or PSG) will complete an additional set of sleep questions ~~during the PSG study setup. It, including includes~~ validated questions on sleepiness (Epworth

Sleepiness Scale; PROMIS Sleep Impairment Scale), sleep quality and insomnia symptoms (Women’s Health Initiative Insomnia Rating Scale Index, Insomnia Severity Index), restless legs symptoms (International Restless Legs Screening Questionnaire), SDB symptoms and sleep duration/timing (SHHS Sleep Habits Questionnaire) and chronotype (a single item from Horne Ostberg and the UKB chronotype question). Thus, questions assess self-reported sleep duration, quality, sleepiness, snoring, circadian preference, and symptoms of sleep disorders (SDB, insomnia and restless legs syndrome).

- **Neck Measurement:** Research assistants will measure the participant’s neck circumference also during the Exam 7 clinic visit or at a home visit during setup of the PSG study using a non-distensible tape measure placed below the laryngeal notch and perpendicular to the long axis of the neck.

#### 6.2.7. *MESA Lung Exam Components*

- **Safety Forms:** Participants will be asked to complete a questionnaire to ensure safety of spirometry and, if selected, administration of albuterol.
- **Pre- & Post-bronchodilator Spirometry:** Spirometry consists of participants inhaling and exhaling as hard and as fast as they can through the mouth. Participants will also be asked to breathe in and out slowly through the mouth. These actions will be repeated at least three times to ensure valid readings. The setup and procedures will take approximately 15 minutes to complete. For in-person clinic visits, a SensorMedics model 1022 rolling-barrel spirometer will be used for all readings, and the procedure will follow American Thoracic Society guidelines. Home visits will use a portable pocket spirometer device. A new mouthpiece will be used for each volunteer. Participants with airflow limitation (prebronchodilator FEV1/FVC ratio  $<0.70$  or  $<LLN$ ) will receive two inhalations of 90 mcg albuterol via MDI and spacer, and will then repeat the spirometry test (“post-bronchodilator spirometry”) for up to an additional 5 minutes. Lung function measured by spirometry is a specific, quantifiable marker of obstructive lung disease. It strongly predicts both pulmonary and cardiac events, including incident heart failure. Post-bronchodilator spirometry is necessary to define chronic obstructive pulmonary disease (COPD), the third leading cause of death. Repeat measures over time define of progression of lung disease. Post-bronchodilator spirometry will only be performed at in-person clinic visits.
- **Non-contrast Full-Lung CT Scan:** Non-contrast, full-lung, MDCT scanning (SOMATOM Flash) of the chest will be performed for approximately 30 minutes to assess the pulmonary emphysema using lung density, bronchial wall thickness, and hyperinflation. Participants with a cumulative exposure in MESA of  $>25$  mSv will be excluded from all CT scanning. The youngest participants will be approximately 60 years old; hence pregnancy is not an issue. The estimated average dose across the whole Lung cohort is 2-3 mSv. The dose varies with body size so is lower in thinner men and higher in heavier women. However, since radiation beams are absorbed by adipose tissue, the effective dose to susceptible organs in heavier participants is likely to be as low or lower than in thinner participants.

- **Hair Follicle Collection:** All participants will be selected for hair follicle collection for an additional 5 minutes. Ten hairs are plucked from the scalp, inserted in a vial and frozen at -80C.
- **Nasal Brushing:** All participants will be selected for nasal brushing for an additional 5-10 minutes. A polyester-tipped flexible soft brush is inserted into one of the participant's nostrils via a nasal speculum, then rotated 180 degrees and withdrawn. The procedure will be repeated once. After swabbing, the brush is cut off, the swab is placed in a vial and frozen at -80C.
- **Environmental Exposures Questionnaire:** Data on home characteristics and environmental exposures will be collected. The daily check-in will take up to 15 minutes to complete.

#### 6.2.8. *MESA Stress Reactivity Exam Components*

- **Heart Monitoring:** Participants will wear a Cardea SOLO ECG heart monitor patch for 7 days. Consent, application of the patch, and delivery of instructions will take approximately 30 minutes to complete at the clinic, home, or remote visit. The device will be returned to sleep study technicians or mailed to the reading center in a pre-paid envelop. If the heart monitor patch is lost or damaged, or if another scientific question arises that could be answered with repeated ECG monitoring, participants may be invited to repeat the monitor.
- **Daily Stress Questionnaire:** Data on daily stressors and positive and negative affect will be collected over the phone or using a self-administered web-based or paper survey for 7 days when participants are wearing the Cardea patch. The daily check-in will take up to 15 minutes to complete.

#### 6.2.9. *Follow-up Phone Calls*

- Clinic staff contact participants by telephone at regular intervals (Follow-up Calls) to ask questions regarding health since the previous telephone interview, specifically those involving a hospitalization, nursing home admission, or diagnosis of myocardial infarction (MI), angina, congestive heart failure (CHF), peripheral arterial disease (PAD), stroke or transient ischemic attack (TIA). The schedule of follow-up phone calls are displayed in the Fourth Contract Period timeline from section 3.2. The 23rd, 24th, and 25th Follow-up phone calls occur during the Exam 7 period.
- The surveillance phone interview in MESA serves several purposes:
  - To ascertain whether participants have experienced any potential events
  - To update tracking data including address, phone number, email address, contact information and secondary contact information
  - To update participants' vital status
  - To obtain information regarding participants' general health and health care treatment since their last MESA telephone Follow-up call or clinic visit
  - To obtain detailed information about specific medical conditions that participants have been reported (by a physician) to have since their last MESA telephone

- Follow-up call or clinic visit
- To obtain detailed information about any procedures or hospitalizations participants have had since their last MESA telephone Follow-up call (not since clinic visit)
- To introduce upcoming exams and schedule an appointment.

### 6.3. Flexibility of Exam Structure

The seventh examination of the MESA contract will include in-clinic, remote, and home visit options for recording data and performing exam components. Given the age and frailty of participants and the ongoing pandemic, the exam will allow maximum flexibility for data collection. The majority of Exam 7 components can be completed at an in-home visit with a study technician, and many could be completed using a remote visit model (sending exam equipment to the participant and talking with a study technician by phone or video conference). Participant questionnaires can be completed in the clinic, by phone with an interviewer, using a web-based survey, or on paper forms at home. The following table summarizes which components can be completed by each type of exam.

**Table 5: Exam Components allowed by each visit type**

[figure not shown]
Component	Study	Visit Type			
		In-clinic	Home	Remote	Phone
Clinic Reception and Consent	All	Yes	Yes	Yes	No
Blood Pressures	Core, MIND	Yes	Yes	No	No
Pulse Oximetry	Core, Lung	Yes	Yes	No	No
Height	Core, MIND	Yes	Yes	No	No
Weight	Core, MIND	Yes	Yes	No	No
Waist circumference	Core, MIND	Yes	Yes	No	No
Neck circumference	MIND, 24hAct	Yes	Yes	No	No
Phlebotomy	Core, 24hAct, Glucose, Lung, MIND	Yes	Yes	No	No
Urine Collection	Core/Lung	Yes	No	No	No
Medications	Core, MIND	Yes	Yes	Yes	No
Medical History	Core, MIND	Yes	Yes	Yes	Yes
Personal History/Demographics	Core	Yes	Yes	Yes	Yes
Arterial Stiffness	MESA-MIND	Yes	No	No	No
Clinician’s Physical Examination		Yes	No	No	No
SPPB		Yes	No	No	No
Cognitive Testing		Yes	Yes	Yes	No
Brain MRI		Yes	No	No	No
PET imaging		Yes	No	No	No
Informant Interview		Yes	Yes	Yes	No
Sleep Questionnaires	MESA Sleep	Yes	Yes	Yes	Yes
Sleep Study/Diary		No	Yes	Yes	No
Actigraphy/Diary		Yes	Yes	Yes	No
Blood Pressure Monitor/Diary		Yes	Yes	Yes	No
Activity and Sleep monitor/Diary	24hACT	Yes	Yes	Yes	No
Physical Activity Questionnaire		Yes	Yes	Yes	Yes
Spirometry exclusion/completion	Lung IV	Yes	Yes	No	No
Pre and post-bronchodilatory spirometry		Yes	Yes (no BD)	No	No
Environmental Exposures Questionnaire		Yes	Yes	Yes	Yes
Nasal brushing		Yes	No	No	No
Hair collection		Yes	No	No	No
Lung CT		Yes	No	No	No

Neighborhood Questionnaire	Neighborhood	Yes	Yes	Yes	Yes
Continuous Glucose Monitor/Diary	Glucose	Yes	Yes	Yes	No
Cardea SOLO Patch	Stress Reactivity	Yes	Yes	Yes	No
Daily Stress Questionnaire		Yes	Yes	Yes	No

Examples of the different exam models are reflected in the next sections. The order of exam components remains flexible based on the priorities of the study and the needs of the participants.

### 6.3.1. Exam 7 In-Clinic Visit Option

The in-clinic visit option allows participants to complete consent over the phone, either signing the consent form via REDCap or by mailing the consent form to the participant for signature. Questionnaires can be completed by phone, paper, or web survey based on participant preference (collected during the consent phone call). The MESA-MIND cognitive assessment can also be administered by phone or video visit, but it will not be collected at the same time as the questionnaires. The in-clinic exam includes components in the list below. Home monitoring is scheduled after the in-clinic exam, with study technicians setting up PSG, activity and sleep monitors, cardiac heart patch, and continuous glucose monitor on day 1. After at least 7 days of wear time, technicians return to the home to pick up the monitors and place the ambulatory blood pressure monitor. After 24 hours of wear, it is returned to the clinic by mail or returned during an imaging visit. CT, MRI, and PET imaging can occur before or after the home monitoring period, but the home monitoring devices cannot be worn during the MRI or PET. Estimated total participant burden is 6.2 hours.

CT, MRI, PET visits occur before or after home monitoring, or during the In-Clinic Exam

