- **Ambulatory Blood Pressure Monitoring:** The 24-hour ambulatory blood pressure monitoring can be uncomfortable because of the repetitive inflation of the blood pressure cuff. Participants may feel discomfort from the blood pressure cuff on their arm when it inflates. During sleep, the cuff may cause sleep disruption. Very rarely, the pressure may damage a nerve in the arm.
- **The following procedures were assessed and do not have any foreseeable risk to participants, beyond the risks of loss confidentiality in the event of a data breach:**
  - **Seated blood pressure**
  - **Anthropometry**
  - **Urine collection**
  - **Collection of personal history/medical history/medications and other questionnaires.**
  - **Completion of home diaries and non-sensitive questionnaires**
  - **Neck measurement**
  - **Pulse oximetry**

Participation in research carries a theoretical risk for some people of being given information that they might prefer not to have heard (for example, some test results) or that may be difficult for them or their health care provider to interpret. This may lead to other tests, which MESA will not pay for.

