### 6.3.2. Exam 7 Home Visit Option

The home visit option also allows participants to complete consent over the phone, either signing the consent form via REDCap or by mailing the consent form to the participant for signature. Questionnaires can be completed by phone, paper, or web survey based on participant preference (collected during the consent phone call). The MESA-MIND cognitive assessment can also be administered by phone or video visit, but it will not be collected at the same time as the questionnaires.

The home exam includes components in the list below. If feasible, the participant can also be invited to come to the clinic after the home visit for scanning and/or other procedures that are not possible during a home visit.

- Consent
- Anthropometry
- Oximetry
- Seated Blood Pressure
- Blood Collection
- Cognitive Assessment
- Questionnaires
- Spirometry
- Monitor device placement and instructions
  - ABPM
  - Hip activity monitor
  - Wrist activity monitor
  - Continuous glucose monitor
  - Heart Monitor Patch
  - Overnight Sleep Study (PSG)

Home monitoring equipment can be set up at the same time as the home exam. After at least 7 days of wear time, the monitors are returned by mail or picked up by study staff. Those who participate in the home visit will not complete hair, nasal brushing or urine collection, arterial stiffness, SPPB, or a physical exam. Estimated total participant burden is 5.4 hours.

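### The device-sequence passages contradict each other: depending on visit option, the ambulatory BP night can lose its wrist record or fall on the polysomnography night

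*Protocol*

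**What the plan says.** **The rules.** Protocol 6.2.6 (24-hour Blood Pressure Monitoring) states that "ABPM will overlap with the one night of wrist sleep monitoring but not with the home sleep study (polysomnography", and places the cuff on the last day of wrist monitoring. The MESA Sleep row of Table 4 agrees: PSG goes with the first wrist day and ABPM with the last. Sections 6.2.3 and 6.2.6 set 8 days of wrist wear, and 6.2.3 sets 8 days of hip wear alongside it.

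**The logistics.**
- In-clinic option (6.3.1): technicians begin by "setting up PSG, activity and sleep monitors, cardiac heart patch, and continuous glucose monitor on day 1". Then: "After at least 7 days of wear time, technicians return to the home to pick up the monitors and place the ambulatory blood pressure monitor". Only the ABPM is described as coming back later, by mail or at an imaging visit.
- 6.2.6 itself says that the ABPM "will be fit during a return home visit (when other equipment is retrieved").
- Home option (6.3.2): ABPM and PSG stand in the same device list, and "Home monitoring equipment can be set up at the same time as the home exam".
- Remote option (6.3.3): the same devices are mailed and applied with guidance. No order is given.
- Sleep diary (6.2.6): participants record when the wrist monitor and the "BP cuff (first night only) is removed".

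**The concern.** The rules in 6.2.6 serve two measurement purposes. A wrist record on the cuff night lets asleep and awake pressures be separated by actigraphy; 6.2.6 says that the wrist device's features help mark sleep onset and offset. Keeping the cuff off the PSG night protects the sleep recording, since 4.2.2 warns: "During sleep, the cuff may cause sleep disruption".

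Staff who follow the visit-option sections or the diary text can defeat either purpose. Without the wrist record, the sleep period on the cuff night rests on diary or clock times. With the cuff on the PSG night, the sleep being measured may be disturbed by the measurement. Section 5.5 makes nocturnal hypertension a mediating pathway between sleep disturbance and cognition, so both measures enter the same analysis. A lost overlap night cannot be recovered later. The failure also differs by visit option, and 6.3 explains the options partly by participants' age and frailty, so measurement error could vary with health.

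**Working it through.** The protocol gives no figure to reproduce: it reports no count of overlap nights and no split of participants by visit option. The check lays the devices on one time line.

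**Inputs.** Time is counted in days elapsed since set-up, so the protocol's day 1 is the interval 0–1.
- PSG: 0–1 (Table 4, first wrist day).
- Wrist monitor: planned 0–8 (6.2.3, 6.2.6).
- ABPM: 24 hours from fitting (6.2.6).
- In-clinic pick-up: 7 days or later, at the visit that fits the ABPM (6.3.1).

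**Formula.** Overlap = max(0, earlier end − later start).

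| Case | Wrist | ABPM | ABPM and wrist | ABPM and PSG |
|---|---|---|---|---|
| In-clinic, literal, pick-up at 7 | 0–7 | 7–8 | max(0, 7−7) = 0 | max(0, 1−7) = 0 |
| In-clinic, literal, pick-up at 8 | 0–8 | 8–9 | max(0, 8−8) = 0 | max(0, 1−8) = 0 |
| In-clinic, pick-up at 7, wrist left on to 8 | 0–8 | 7–8 | 8−7 = 1 | 0 |
| Home or remote, ABPM at common set-up | 0–8 | 0–1 | 1−0 = 1, on the first day | 1−0 = 1 |
| Home or remote, ABPM on the eighth day | 0–8 | 7–8 | 8−7 = 1 | max(0, 1−7) = 0 |

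**Reading the table.**
1. In-clinic, the wrist overlap is zero whenever pick-up and fitting share a visit and the wrist device is taken. Moving the visit from 7 to 8 days does not help. At 7 days, the wrist and hip records are also 8 − 7 = 1 day short.
2. In-clinic, the PSG rule is met in every case.
3. In the home and remote options, fitting everything at once gives one shared PSG night and puts the cuff on the first wrist day instead of the last. Deferring the cuff meets both rules, but neither section says to defer it.
4. The diary's cuff night is the interval 0–1, the PSG interval in Table 4. That contradicts the last-day placement in any visit option.

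**Exposure on a shared night.** 6.2.6 programs readings every 30 minutes. For an assumed 8-hour night, 8 / 0.5 = 16 inflations; each hour more or less changes this by 1 / 0.5 = 2.

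**The case against.** The strongest reply is that the intended order is already stated. Table 4 and 6.2.6 fix it without limiting it by visit type. The text after Table 5 presents 6.3.1–6.3.3 as examples with a flexible order. In 6.2.6 the end-of-period timing is called typical, and the wrist overlap is asked for only as far as possible. A benign reading of 6.3.1 also exists: 7 days plus 24 hours of ABPM makes the 8 wrist days, with only the other devices collected at the visit.

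Part of this stands. The intended order is clear, and the benign reading satisfies both rules. But 6.3.1 does not say it. The prepaid mailer for the wrist device in 6.2.6 applies unless a technician retrieves it at a home visit, which is the 6.3.1 situation. Nothing in the reply explains the diary's first night.

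Four stronger readings are tempting and not supported:
- **Both rules fail together.** No option necessarily breaks both. In-clinic keeps ABPM away from PSG. The home text only permits a common set-up.
- **The pick-up cuts glucose monitoring short.** Section 6.2.4 asks for wear of the "FreeStyle Libre Pro CGM from Abbott) for up to 14 days" and Table 4 gives 7–14 days, so an end at day 7 is allowed. Only the Table 1 label says 14 days. Any precision loss counted against 14 days uses a target that the protocol does not set for everyone.
- **Visit type follows cognition.** Section 6.3 names age, frailty and the pandemic, not cognition.
- **A 7-day activity record is unusable.** For short records, repeat wear is foreseen only below 5 days (6.2.3, 6.2.6).

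**Conclusion.** The protocol is wrong as written on device order, and the error is one of wording. Followed literally, the in-clinic option gives 0 days of wrist and ABPM overlap where 1 is required. The home and remote options allow 1 shared ABPM and PSG night where none is allowed. The diary text names the wrong night throughout.

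This rests on reading the monitors collected in 6.3.1 as including the wrist monitor, which that section sets up on day 1 and does not exempt. The number affected cannot be derived: it lies between 0 and the 1,800 that MESA Sleep aims for, depending on the visit-option mix and on what staff do in practice. Diaries are collected in any case, so sleep timing on the cuff night would be measured less well, not lost. That the cuff disturbs sleep on a shared night is a possibility that the protocol concedes, not a measured effect.

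**What to change.** Bring 6.2.6 and 6.3.1–6.3.3 into line with Table 4:

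1. In 6.3.1, and in the fitting sentence of 6.2.6, state that the wrist monitor stays on through the ABPM night as the last of its 8 days. It is then returned with the ABPM, in the prepaid mailer or at an imaging visit.
2. State in all three visit options that ABPM is not worn on the PSG night. Where home or remote equipment is supplied at once, say that the cuff waits for the last wrist day.
3. In the diary text, replace the first night with the ABPM night.
4. Say whether the hip monitor also stays on for its eighth day or whether 7 days are accepted when pick-up is at 7.

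A rule that pick-up be no earlier than day 8 should not be added: with the wrist device kept on for the cuff night it would give 8 + 1 = 9 days against the stated 8.

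The cost is wording and use of a mailer that 6.2.6 already provides. The downside is that the wrist device comes back by post or at a later visit instead of at the technician's pick-up.
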